### 14.1 Sample Size

12 participants.

### 14.2 Randomisation

N/A

### 14.3 Analysis

Planned analyses include; descriptive statistics, visually inspecting graphs, the Tau statistic, and reliable change (Jacobson & Truax, 1991).

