#### 7.1.2 Secondary endpoints

### 7.2 Trial Design

A nonconcurrent multiple baseline case series (A1BA2) design will be utilised. Participants will be randomised to a baseline of 1-3 weeks symptom monitoring before receiving three sessions of ImRs and two weeks follow-up.

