### 7.3 Trial Flowchart

	Recruitment visit	Assessment visit	Waitlist 1-3 weeks	Treatment period 3 weeks	Week 1 post treatment	1-week appointment post-treatment	Week 2 post-treatment
Patient information	X						
Informed consent		X					
30-minute Semi-structured interview		X					
Psychotic Symptom Rating Scale (PSYRATS)		X					
The Warwick-Edinburgh Mental Well-Being Scale (WEMWBS)		x				x	
The Posttraumatic Diagnostic Scale for DSM-5 (PDS-5)		x				x	
Mini-Trauma and Life Events Checklist (mini-TALE)		x					
Credibility and Expectancy				x			

The electronic version of this document is the latest version. It is responsibility of the individual to ensure that any paper material is the current version. Printed material is uncontrolled documentation.

Questionnaire (CEQ)							
Client Satisfaction Questionnaire (CSQ-8)						x	
Daily trauma index memory dimensions			x		x		x
Imagery Rescripting				x			

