#### **10.4 Randomisation Procedure / Code Break**

Participants will be randomised to a waitlist time of 1, 2, or 3 weeks. Randomisation will occur at assessment using a computer program.

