## 14. Statistics

Through using a multiple baseline case series design, a waitlist period will control for demand characteristics and effects of time, talking about previous trauma and completing measures. Furthermore, a protocol has been developed for the assessments in order to ensure consistency. Data will not be analysed until all data is collected. Finally, this project will be registered on [clinicaltrials.gov](http://clinicaltrials.gov), ensuring that the method and data-analysis is predetermined.

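### Section 14.3 names no formal analysis that uses the randomised 1-, 2- or 3-week baselines, so this document does not formally secure the control for effects of time claimed in Section 14

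*Combined protocol and SAP*

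**What the plan says.** Section 7.2 sets the design: "A nonconcurrent multiple baseline case series (A1BA2) design will be utilised". Section 10.4 adds the random element: "Participants will be randomised to a waitlist time of 1, 2, or 3 weeks". Section 11.1 confirms that a computer makes the allocation after the initial assessment. It also requires four 0-100 ratings of the index memory every day, including during the treatment weeks and for two weeks afterwards.

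Section 14 states the purpose of the stagger: "a waitlist period will control for demand characteristics and effects of time, talking about previous trauma and completing measures". Section 6 uses the same argument to set this study apart from earlier work on rescripting trauma memories in voice hearers, which it faults for incomplete control of time.

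Section 14.3 lists the analyses: "Planned analyses include; descriptive statistics, visually inspecting graphs, the Tau statistic, and reliable change". It does not say which Tau is meant, which phases it compares, or how participants are combined. The section headed "14.2 Randomisation" reads only N/A, so the allocation ratio and any blocking are not stated. Section 14 adds "Data will not be analysed until all data is collected" and says that public registration will fix the method and analysis in advance.

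**The concern.** Staggered baselines control for time only if the analysis asks whether change follows each person's own start of treatment rather than time since assessment. Randomising the lengths makes a formal test of that possible, but Section 14.3 names none.

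An analysis within one person cannot separate the two unaided, because the treatment days always come later than the baseline days. Steady improvement from time, assessment or daily monitoring could then be reported as impact of imagery rescripting. The protocol recognises that risk: Section 6, under Benefit, notes that control participants also improved in trials of trauma-focused therapy for psychosis, although it gives no size.

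**Working it through.** **1. The plan's own figures.** Shortest participation is 1 + 3 + 2 = 6 weeks (42 days) and longest is 3 + 3 + 2 = 8 weeks, as Section 11.1 states. The 12 participants in Section 14.1 come with no inputs, so that number cannot be reproduced. The plan gives no SD, drift, autocorrelation, effect size or scale reliability. All values of these below are assumptions.

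**2. Which listed methods use the baseline lengths.**
- Descriptive statistics: no use is specified.
- Visual inspection: it can use the stagger, but informally and with no decision rule.
- Reliable change: assessment is compared with the appointment one week after treatment, 1 + 3 + 1 = 5 to 3 + 3 + 1 = 7 weeks later, with no untreated comparison. The threshold is 1.96 × √(2(1 − r)), which is 1.24 SD of the questionnaire at reliability r = 0.8 and 0.88 SD at r = 0.9. Drift alone reaches it at 1.24/7 to 1.24/5 = 0.18 to 0.25 SD a week, or 0.88/7 to 0.88/5 = 0.13 to 0.18 SD a week.
- Tau: this depends on the variant (step 3).

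**3. Tau with drift and no treatment effect.** Tau = S/(mn), where S is the number of pairs of one baseline day and one later day that show improvement, minus the number that show worsening. Daily series were simulated with SD 1, lag-1 autocorrelation (AR) 0 to 0.6, and phases A1 of 7, 14 or 21 days, B of 21 and A2 of 14. The drift was 1 SD over six weeks.

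| Baseline days | Mean A1 v B | Mean A1 v A2 | Theil-Sen-corrected A1 v B: share beyond ±0.5 (AR 0-0.4) |
|---|---|---|---|
| 7 | about 0.19 | about 0.41 | 74-79% |
| 14 | about 0.23 | about 0.45 | 46-59% |
| 21 | about 0.28 | about 0.48 | 28-44% |

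Halving the drift gives 0.09 to 0.15 for A1 v B. The Theil-Sen-corrected Tau averages -0.01 to 0.02, so its problem is imprecision, not bias.

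Another common correction subtracts the baseline's own S before dividing by mn. It was tried with drift of 2 points a week, day-to-day SD 10, independent days, and baseline against all 35 later days. It barely changed the result: 0.32/0.37/0.42 became 0.31/0.36/0.39. The variant therefore matters.

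**4. What a test using the lengths does.** For person i and baseline of w weeks, let D_i(w) be the mean rating on days 1 to 7w minus the mean on days 7w+1 to 42. Sum D_i over participants at their actual lengths, and compare the total with its value under every other allocation. With 4/4/4 there are 12!/(4!)³ = 34,650 allocations. One participant alone has 3, so the smallest p-value is 1/3 and the test must pool.

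With no treatment effect it rejected in 4 to 6.5% of runs at a nominal one-sided 5%, with and without drift.

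Power for an abrupt effect at the chosen change-point (n = 12, AR 0.4, complete ratings):
- 1 SD in everyone: about 95%.
- Mean 1 SD, varying between people with SD 1: about 80-85%.
- 0.5 SD in everyone: about 50-55%.
- Change-point at the wrong session: near-blind, rejecting about as rarely as under no effect.

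A statistic that takes the larger of a step and a two-week ramp was also run at the matching change-point, with 1 SD in everyone:
- Abrupt effect: 92-94%.
- Gradual effect: 59%.
- Abrupt effect, 40% of ratings missing at random: 82-85%.
- Abrupt effect, sessions up to six days late: about 70%.
- Abrupt effect, six participants (the lower end of the synopsis range): 58-64%.

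**The case against.** This is a small exploratory series run as a doctoral thesis, with no stated alpha or success criterion. Visual inspection of randomly staggered series is a way of using the stagger. The list in Section 14.3 is worded as inclusive, not exhaustive, and Section 14 says registration will predetermine the analysis. Tau may be meant in a trend-corrected form, and the drift assumed here comes from no figure in the plan.

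Much of this stands, and it limits the point. A reader might infer that time is not controlled at all, or that the conclusions will rest on visual judgement alone. The documents do not support that: the randomised stagger is in place, and the registered analysis could not be consulted. Nor is it right that any Tau would credit drift to treatment, because the Theil-Sen form does not do so on average.

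What the objection does not remove is the mismatch within this document. Sections 6 and 14 make a firm claim about time, and the analyses named here give it no formal support.

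**Conclusion.** The point holds as a should-fix item. No analysis named in Section 14.3 formally uses the randomised baseline lengths, although Section 14 presents control for time as secured. The gap concerns the impact half of the aim and leaves feasibility untouched.

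The direction of the bias in an uncorrected within-person Tau follows from the design; its size depends on the assumed drift and SD. It would also be too strong to infer that a randomisation test would settle the matter. Power is high only for a large, abrupt, fairly uniform effect at the change-point chosen, and a non-significant result would not be evidence of no effect.

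**What to change.** 1. In Section 14.3, before any data are analysed, add one group-level randomisation test on one named daily rating over days 1-42, which every allocation covers. Re-allocate the lengths by the method actually used. Choose one statistic and one change-point in advance, with the reason: session 1 (the A1/B boundary) or session 2 (where Section 8.1 begins rescripting the trauma memory). Replace N/A in Section 14.2 with the allocation method.
2. Keep Tau as a descriptive effect size. Name the variant and the phases, and attach no p-values that assume independent days.
3. State the limits. Inference is at group level. The test separates treatment from time, not the content of imagery rescripting from therapist contact. Power falls with a wrong change-point, gradual or variable effects, missing ratings, late sessions or fewer participants.
4. If no such test is added, reword Section 14 to say that the staggered baselines allow an informal, visual check on effects of time.

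The cost is protocol wording and one short script, with no extra participants, visits or ratings beyond those Section 11.1 requires. The downside is a little more analysis work and no verdict for individual participants.

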## 15. Trial Steering Committee

N/A

## 16. Data Monitoring Committee

N/A

## 17. Direct Access to Source Data and Documents

The Investigator(s) will permit project-related monitoring, audits and REC review by providing the Sponsor(s), and REC direct access to source data and other documents.

## 18. Ethics & Regulatory Approvals

The project will be conducted in compliance with the principles of the Declaration of Helsinki (1996), the principles of GCP and in accordance with all applicable regulatory requirements including but not limited to the Research Governance Framework and the Mental Capacity Act 2005.

This protocol and related documents will be submitted for [review to South London and the Maudsley Research Ethics Committee \(REC\)](#)

The research therapist will submit a final report at conclusion of the trial to the CAG, REC, and the Sponsor

It is expected that the all approvals will be completed, and the research will commence on 01/05/2018.

## 19. Quality Assurance

Monitoring of this trial will be to ensure compliance with Good Clinical Practice and scientific integrity will be managed by the project team. Research supervisors will listen to part or full therapy session recordings to ensure they meet a high-quality standard.

## 20. Data Handling

The Chief Investigator will act as custodian for the trial data. The following guidelines will be strictly adhered

The electronic version of this document is the latest version. It is responsibility of the individual to ensure that any paper material is the current version. Printed material is uncontrolled documentation.

to:

Patient data will be anonymised.(amend as required)

- All anonymised data will be stored on a password protected computer.
- All trial data will be stored in line with the Data Protection Act.
- and archived in line with Sponsor requirements

## **21. Data Management**

Data will be collected on paper files, and stored on computer software, including Microsoft excel and SPSS

### **21.1 Access to Medical Records**

In order to confirm the diagnosis given to the participants and to record their participation in the project for their care team the researcher will need to access the patient's electronic medical records, with the consent of the participant, through the electronic Patient Journey System within SLaM.

### **21.2 Personal Data**

Information such as names, addresses and telephone numbers will be needed to contact participants both to arrange appointments and complete measures between appointments. It will be stored separately from the anonymised data and it will not be possible to link this data to that which is collected during the project.

### **21.3 Audio/Visual Recording**

Participants will be audio-recorded during their therapy and assessment sessions, they will be asked to sign a separate consent form for these recordings. Participants will be recorded using a password protected, encrypted mobile phone and the research therapist will ensure no identifiable information beyond the memories themselves is recorded. This mobile will be stored in a locked filing cabinet at Kings College London when not in use by the research therapist, and recordings will be stored on Office 365 as soon as the research therapist returns to the office environment. GPS will be activated on the phone and remote lock and erase will be enabled.

### **21.4 Manual Files**

All data will be collected using paper questionnaires and interviews - these will be identified using participant codes only and will not contain any identifiable information.

### **21.5 University Computers**

All data will be entered onto Kings College London computers and password-protected

## **22. Publication Policy**

This project is part of a doctoral thesis and will be written up as part of the written requirement. It is intended that the results of the project will be reported and disseminated at international conferences and in peer-reviewed scientific journals.

## **23. Insurance / Indemnity**

The lead sponsor, King's College London, will take primary responsibility for ensuring that the design of the project meets appropriate standards and that arrangements are in place to ensure appropriate conduct and reporting. King's College London also provides cover under its No Fault Compensation Insurance, which provides for payment of damages or compensation in respect of any claim made by a research subject for bodily injury arising out of participation in a clinical trial or healthy volunteer study (with certain restrictions). The co-sponsor, South London and Maudsley NHS Foundation Trust, takes responsibility for ensuring that appropriate standards, conduct and reporting are adhered to regarding its facilities and staff involved with the project.

## 24. Financial Aspects

This project is conducted for part-fulfilment of the Doctorate in Clinical Psychology thesis – it will receive £1000 funding from the course for this purpose.

## **27. Appendices – see separate documents**

### **27.1 Participant Information Sheet**

### **27.2 Consent form**

### **27.3 Therapy Information Sheet**
